**Table 5.3.1 Titration Scheme for 20 mg Daily Dose**

Kit Assigned on Visit/Day	First Dose		Second Dose	
Visit 2, Day 1	20 mg Placebo	10 mg	20 mg Placebo	10 mg Placebo
Visit 3, Day 8	20 mg Placebo	10 mg	20 mg Placebo	10 mg
Visit 4, Day 15	20 mg Placebo	10 mg	20 mg Placebo	10 mg
Visit 5, Day 22	20 mg Placebo	10 mg	20 mg Placebo	10 mg
Visit 6, Day 29	20 mg Placebo	10 mg	20 mg Placebo	10 mg

**Table 5.3.2 Titration Scheme for 40 mg Daily Dose**

Kit Assigned on Visit/Day	First Dose		Second Dose	
Visit 2, Day 1	20 mg Placebo	10 mg	20 mg Placebo	10 mg Placebo
Visit 3, Day 8	20 mg Placebo	10 mg	20 mg Placebo	10 mg
Visit 4, Day 15	20 mg	10 mg Placebo	20 mg Placebo	10 mg
Visit 5, Day 22	20 mg	10 mg Placebo	20 mg	10 mg Placebo
Visit 6, Day 29	20 mg	10 mg Placebo	20 mg	10 mg Placebo

Subjects randomized to placebo will receive the 10 mg and 20 mg placebo capsules for the first and second dose (4 capsules/day) during the trial.

**Visit 7, Day 36:** End of Study Visit

**Visit 8:** Follow-up Phone Call

#### **5.4 Randomization and Blinding Procedures**

All study medication will be supplied in weekly blister packs and will be similar in color, smell, taste, and appearance, thereby enabling double-blind conditions.

Enrollment will occur at Visit 2, upon randomization, after all screening procedures have been performed and eligibility for the study is confirmed at the Baseline Visit.

For the randomization of subjects, the Investigator or delegated designee will complete the randomization electronic case report form (eCRF), which is integrated with the study interactive web response system (IWRS). The IWRS will assign subjects to a treatment group (placebo, 20 mg, or 40 mg AR19/day) based on the pre-defined randomization list.

Randomization will occur via IWRS at Visit 2, if a subject meets all inclusion and no exclusion criteria. Subjects will be randomized 1:1:1 to placebo or 20 or 40 mg AR19/day. Randomization will take place according to a fixed schedule using a permuted block design with no stratification by clinical site.

### **5.5 Emergency Unblinding of a Randomization Code**

Unblinding should occur only when knowing the treatment assignment has a bearing on the medical treatment or evaluation of a subject. Whenever possible, the need to unblind should be discussed with the Medical Monitor prior to unblinding. In the event of an emergency, the Investigator, Pharmacist, or designated qualified individual may obtain the subject's blinded treatment via IWRS. If an individual designated to perform emergency unblinding does not have access to the IWRS, Sponsor designee may be contacted and can perform the unblinding for that individual.

A subsequent written report, including all pertinent details, must be submitted to the Medical Monitor within 1 business day of the unblinding. Whenever possible, the blind of the subject should be maintained.

If an Investigator, site personnel performing assessments, or subject is unblinded, the subject must be withdrawn from the study, and procedures accompanying withdrawal should be performed.

### **5.6 Study Drug Adjustments**

Subjects who cannot tolerate their daily dose of AR19 (up to 20 or 40 mg daily) will be discontinued from the study. Study drug dose adjustments are not allowed during this fixed dose study.

### **5.7 Drug Accountability**

The Investigator or designee will verify and acknowledge receipt of study drug. All study medication must be stored in a secure area under the proper storage requirements with limited access (i.e., restricted to the Investigator or designees). Study medication designated for this clinical study must not be taken by anyone other than those enrolled in this specific investigation and may not be utilized for any laboratory or animal research. All study medication dispensed to subjects must be accurately recorded on the Drug Accountability Record maintained at the study center. Subjects should be instructed to return all study medication dispensed to them (including any unused capsules and blister cards) at each study visit.

Drug accountability will be performed at each study visit starting with Study Visit 3. At each visit, subjects should return all unused medication dispensed to them at the prior visit. All study medication and blister cards will be retained at the site for study monitor

verification. All study medication should be stored at the study site until further instruction from the study monitor.

The Investigator is responsible for returning all unused or partially used study medication to the Sponsor's designee at the end of the study. The Investigator must verify that all unused or partially used study medication supplies have been returned by the subject and that no remaining supplies are in the Investigator's possession at the time of study discontinuation.

Arbor or designee will provide detailed drug accountability instructions at the start of the study.

## **5.8 Treatment Compliance**

Subject training at the Baseline Visit (Visit 2) and subsequent ongoing retraining regarding proper dosing of study medication will occur to ensure subject compliance. Beginning with Visit 3, study staff will assess compliance at every study visit to confirm that the subject is taking study medication according to the protocol. Compliance is defined as taking 80% to 100% of study medication for the duration of the study.

## **5.9 Prior, Concomitant, and Prohibited Medications**

### **5.9.1 Prior Medications**

Subjects who were taking a prescription psychotropic medication other than a stimulant or sedative hypnotic at the time of Screening are not eligible for the study. Subjects who have recently taken prescription psychotropic medications for ADHD (except stimulants or sedative hypnotics) are eligible, if the psychotropic medication will be discontinued at least 28 days prior to the Baseline Visit. Any non-study ADHD stimulant medication must be discontinued at least 7 days prior to the Baseline Visit 2. Subjects must not have participated in any other clinical study in which an investigational drug was administered within 60 days of the Screening Visit and must not participate in other investigational trials during this study.

### **5.9.2 Concomitant Therapy**

Information on concomitant medications will be collected at each study visit through the Post Withdrawal Follow-Up Phone Call (Visit 8) or early termination.

Intermittent use of acetaminophen or non-steroidal anti-inflammatory medications is allowed. Use of non-sedating antihistamines, including Zyrtec, Claritin, and Allegra, as well as Nasonex will also be allowed during the trial. Acetaminophen is permitted for control of fever or pain, if needed. Short courses of prescription and non-prescription medications for treatment of acute illnesses such as the common cold, viral illnesses, and ear infections are permitted, provided they do not contain the medications listed in [Appendix B](#) of the protocol.

If a subject discontinues from the study early, study drug is to be discontinued for at least 24 hours prior to his/her beginning new ADHD therapy.

### **5.9.3 Prohibited Medications**

Use of psychotropic medications, including but not limited to anticonvulsant, antidepressant, anxiolytic, and antipsychotic medications, is not allowed during the study, except for sedative hypnotics used at a stable dose at bedtime only, for at least 30 days prior to Baseline Visit 2. Stimulants (other than study drug) must be discontinued 7 days prior to Baseline Visit 2. Non-stimulant ADHD medications (guanfacine, bupropion, clonidine, and/or atomoxetine) are not allowed within 30 days of Visit 2 or at any time during the study. Prescription or non-prescription cold and/or allergy medications and herbal preparations with sedative effects (such as first-generation antihistamines) or with stimulant or pressor effects (such as pseudoephedrine or ephedrine) are also prohibited. Systemic corticosteroids are prohibited; inhaled or topical corticosteroids are not prohibited. Subjects are not to use an investigational medication from another trial during the study or for the 60 days prior to study start. Prohibited concomitant medications can be resumed after Study Visit 8.

A list of concurrent medication classes that are excluded can be found in [Appendix B](#).

## **6 CLINICAL EVALUATIONS**

### **6.1 Study Procedures**

A detailed schedule of events is located in [Table 6.1.1](#).

Approximately 312 adult subjects, aged 18 to 55 years inclusive at Screening, with a diagnosis of ADHD per DSM-5™ criteria will be eligible for participation in this study. A maximum of 50 mL of blood will be drawn from subjects throughout the study duration.

**Table 6.1.1 Schedule of Events**

Visit Name a	Screen	BL	Week 1	Week 2	Week 3	Week 4	End of Study Week 5	Follow-up Phone Call Week 6	Early Termination
Visit Number	1	2	3	4	5	6	7	8	
Study Day Assessment	-30 to -1	1	8 ±2d	15 ±2d	22 ±2d	29 ±2d	36 ±2d	7 days post V7 +2d	
Subject consent	X								
Eligibility assessment	X	X							
Previous medications	X								
Medical history	X	X							
Demographics	X								
MINI	X								
CAADID	X								
DSM-5™ diagnosis	X								
AISRS	X	X	X	X	X	X	X		X
CGI-S	X	X	X	X	X	X	X		X
CGI-I			X	X	X	X	X		X
Height	X								
Body weight	X	X					X		X
BMI	X								
Vital signs b	X	X	X	X	X	X	X		X
12-lead ECG	X						X		X
Physical examination	X						X		X
Hematology	X						X		X
Serum chemistry	X						X		X

Visit Name a	Screen	BL	Week 1	Week 2	Week 3	Week 4	End of Study Week 5	Follow-up Phone Call Week 6	Early Termination
Visit Number	1	2	3	4	5	6	7	8	
Study Day Assessment	-30 to -1	1	8 ±2d	15 ±2d	22 ±2d	29 ±2d	36 ±2d	7 days post V7 +2d	
Blood alcohol	X								
HbA1c	X								
Pregnancy c	X	X		X		X	X		X
Urinalysis	X						X		X
CYP 2D6 testing d		X							
Drugs of abuse test	X	X							
C-SSRS (BL)	X								
C-SSRS (FU)		X	X	X	X	X	X		X
BRIEF-A		X					X		X
DERS		X					X		X
ASQ		X					X		X
PK Sampling						X	X		
Dispense study drug/training		X	X	X	X	X			
Drug accountability			X	X	X	X			X
Adverse events			X	X	X	X	X	X	X
Concomitant medication	X	X	X	X	X	X	X	X	X

a The interval between each visit for Visits 3-6 must not exceed 9 days.

b At all visits, vital signs include blood pressure and pulse assessments (in triplicate via automated machine). At Screening, vital signs also include respiratory rate and temperature.

c Females of childbearing potential only. Serum pregnancy test will be performed at Visit 1. Urine dipstick pregnancy test is performed onsite at Visits 2, 4, 6, and 7 or early termination and may be performed at any time during study participation, if pregnancy is suspected.

d CYP 2D6 genetic testing for randomized subjects who opt in only. Subjects choosing to opt out are still eligible for the study.

AISRS = Adult ADHD Investigator Rating Scale; ASQ = Affective Style Questionnaire; BL = baseline; BMI = body mass index; BRIEF-A = Behavior Rating Inventory of Executive Function – Adult Version; CAADID = Conners Adult ADHD Diagnostic Interview for DSM-IV; CGI-I = Clinical Global Impression of Improvement; CGI-S = Clinical Global Impression of Severity; C-SSRS = Columbia Suicide Severity Rating Scale; CYP = cytochrome P450; DERS = Difficulties in Emotion Regulation Scale; DSM-5™ = Diagnostic and Statistical Manual of Mental Disorders, Fifth Edition; ECG = electrocardiogram; FU = follow-up; HbA1c = glycosylated hemoglobin; MINI = Mini International Neuropsychiatric Interview for Adults; PK = pharmacokinetic

### **6.1.1 Screening Visit – Study Visit 1 (Day -30 to -1)**

Before any study-specific procedures are performed, the subject must receive an explanation of all study procedures and must sign and date an Institutional Review Board (IRB)-approved written informed consent form. A subject ID number will be assigned at the Screening Visit (Visit 1), for any subject who signs an ICF.

The timing of the Screening Visit must take into account planned absences at the clinical site and the timing of the study visits according to the Schedule of Events [Table 6.1.1](#).

The Screening Visit may be split into more than one calendar day if needed, if all required assessments are performed within 30 days of Baseline (Visit 2).

Diagnosis of ADHD based on DSM-5™ criteria and the CAADID will be confirmed for all subjects at entry by a physician or mental health profession (Master's level or higher), having at least five years of experience using ADHD rating scales for assessment of ADHD and also using the DSM for assessment of psychiatric disorders. A MINI-7.0.2 will be administered on all subjects to assist in screening for other mental health disorders that may be exclusionary.

Following confirmation of appropriate age at the Screening Visit, a diagnosis of ADHD consistent with DSM-5™ criteria will be confirmed prior to the evaluation of other inclusion and exclusion criteria.

During the Screening Period, the following activities will be performed:

- Obtain subject informed consent
- Review of inclusion/exclusion criteria
- Review of medical history
- Review of medication history (ADHD stimulant medication should be discontinued 7 days prior to the Baseline Visit)
- Demographics
- Completion of the following diagnostic criteria for ADHD performed by a physician or mental health professional (Master's Level or higher) with the required experience as outlined above:
  - CAADID
  - DSM-5™ Diagnoses
- Mini International Neuropsychiatric Interview (MINI) 7.0.2
- AISRS
- CGI-S
- C-SSRS Baseline Visit version
- Height, body weight, and body mass index (BMI)
- Blood pressure and pulse (in triplicate via automated machine), respiratory rate, and temperature
- Resting 12-lead ECG
- Physical examination
- Laboratory tests (see [Appendix A](#))

- Serum chemistry panel (including serum pregnancy test for females of child-bearing potential)
- Hematology
- Urinalysis
- Urine drug screen for drugs of abuse testing (performed at the site)
- Blood alcohol level
- HbA1c

Blood and urine samples MUST be drawn after all other assessments are completed.

### **6.1.2 Baseline – Study Visit 2 (Day 1)**

Once the subject is determined to be initially eligible during Screening, the Baseline (Study Visit 2, Day 1) evaluations will be completed. The timing of the Baseline Visit (Day 1) must take into account the need for study visits to occur according to the Schedule of Assessments (see [Table 6.1.1](#)).

If the subject continues to meet eligibility criteria at the Baseline Visit (Day 1), enrollment of the subject into the study will be performed by randomizing the subject through the integrated IWRS/eCRF. Double-blind study medication will be dispensed by the site pharmacy or designated, qualified study personnel (see Section [5.2](#)).

Subjects will be instructed to start taking study medication on the morning of Day 2 with the first dose administered in the morning and the second dose four to six hours later. Subjects will be instructed to return all unused study medication with blister card at the next scheduled study visit.

The following activities will be performed pre-randomization:

- Review of inclusion/exclusion criteria
- Review of medical history
- Body weight
- Blood pressure and pulse (in triplicate via automated machine)
- C-SSRS since last visit
- AISRS
- BRIEF-A
- CGI-S
- DERS
- ASQ
- Concomitant medications assessment
- Urine pregnancy test for females of child-bearing potential
- Urine drug screen for drugs of abuse testing, performed at site
- eCRF entry for randomization

The following activities will be performed post-randomization:

- Cytochrome P450 (CYP) 2D6 genetic testing will be performed only for those randomized subjects who opt in. Subjects who opt out are still eligible for the study.

- Study drug dispensing and study medication training

#### **6.1.3 Treatment Period – Day 2 to Day 36 (±2)**

Enrolled subjects will begin taking study medication at home the morning following the Baseline Visit at 10 mg/day or placebo. From Day 2 through Day 36 (±2) inclusive, subjects will swallow study medication (2 capsules) once daily in the morning with or without food, and again four to six hours later. The dosing regimen will be twice daily for the duration of the study (4 capsules/day).

The following activities will be performed at each visit:

- Blood pressure and pulse (in triplicate via automated machine)
- AISRS
- CGI-S
- CGI-I
- Follow-up C-SSRS
- Adverse events assessment
- Concomitant medications assessment
- Pharmacokinetic sampling\* (Visit 6 only)
- Urine pregnancy test for females of child-bearing potential (Visits 4 and 6 only)
- eCRF entry for study drug assignment
- Study drug accountability and study medication training
- Dispense study drug

\*Blood for pharmacokinetics (Visit 6 only) MUST be drawn after efficacy and safety assessments are completed. Subjects should be instructed to record accurate dosing history (date/time) on their dosing card for the day prior to and day of their study visit.

#### **6.1.4 End of Study – Visit 7/Day 36**

The following activities will be performed during Study Visit 7 / End of Study:

- Blood pressure and pulse (in triplicate via automated machine)
- Body weight
- AISRS
- BRIEF-A
- DERS
- ASQ
- CGI-S
- CGI-I
- Follow-up C-SSRS
- Resting 12-lead ECG
- Physical Examination
- Laboratory tests
  - Pharmacokinetic sampling
  - Serum chemistry panel
  - Hematology

- Urinalysis
- Urine pregnancy test for females of child-bearing potential
- AE assessment
- Concomitant medications assessment
- eCRF entry for study completion
- Study drug accountability

**Blood and urine samples MUST be drawn after efficacy and safety assessments are completed.**

#### **6.1.5 Early Termination**

Every effort should be made to have subjects who withdraw early from the trial return to the site to complete an Early Termination Visit and return any unused study drug.

The following activities should be performed:

- Blood pressure and pulse (in triplicate via automated machine)
- Body weight
- Physical examination
- Resting 12-lead ECG
- Laboratory tests
  - Serum chemistry panel
  - Hematology
  - Urinalysis
  - Urine pregnancy test for females of child-bearing potential
- AISRS
- BRIEF-A
- DERS
- ASQ
- CGI-S
- CGI-I
- Follow-up C-SSRS
- AE assessment
- Concomitant medications assessment
- eCRF entry for early withdrawal
- Study drug accountability

#### **6.1.6 Unscheduled Visit**

Unscheduled visits are allowed if a safety concern is identified.

The following activities may be performed, including but not limited to:

- Blood pressure and pulse (in triplicate via automated machine), respiratory rate, and temperature
- Physical examination, including body weight
- Resting 12-lead ECG
- Laboratory tests (see [Appendix A](#))

- Serum chemistry panel
- Hematology
- Urinalysis
- Urine pregnancy test for females of child-bearing potential
- Any other safety assessments per Investigator's clinical judgment
- AE assessment
- Concomitant medications assessment
- Study drug accountability and study medication training, if needed

### **6.1.7 Post-Withdrawal Follow-Up Telephone Call – Visit 8**

**The following activities will be performed during a follow-up telephone call, 7 + 2 days after Visit 7, for subjects who complete the study:**

- AE assessment
- Concomitant medications assessment

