## **7 ADVERSE EVENTS**

### **7.1 Definition of an Adverse Event**

An AE is defined as “any untoward medical occurrence in a patient or clinical investigation subject administered a pharmaceutical product that does not necessarily have a causal relationship with this treatment.” An AE can therefore be any unfavorable and unintended sign (including an abnormal laboratory finding), symptom, or disease temporally associated with the use of a medicinal (investigational) product, whether or not related to the medicinal (investigational) product. This includes any newly occurring event or previous condition that has increased in severity or frequency since the administration of study drug.

Adverse events will be identified at the times indicated in the schedule by asking the subject a neutral question such as: “How have you been feeling since your last visit?” Adverse events may also be reported spontaneously at any time. Any adverse or unexpected events, signs, or symptoms will be fully recorded on the AE form in the eCRF including details of onset, resolution, frequency, severity (as defined below), seriousness, relationship to the drug, effect on the study drug, treatments administered, and outcome. Any AE that occurs during the study will be followed, whenever possible, until it returns to the baseline condition or becomes stable with no further change expected.

Beginning with the first dose of study drug on Day 2, all AEs occurring up to study completion, must be recorded in the eCRF. All changes in health occurring prior to study drug dosing should be recorded as medical history.

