### **7.3 Collection of Adverse Events**

The collection of AE information will start with the first dose of study drug (Day 2) and continue through the post-withdrawal follow-up phone call (i.e., 7 days after Visit 7). The collection of SAE information will start with the first dose of study drug (Day 2) and continue 30 days after the subject's last dose of study drug. For subjects who terminate early, all AEs and SAEs should be treated as medically appropriate. Should a subject have an ongoing SAE at the last study contact or has an SAE within 30 days after Visit 7, the subject will continue to be followed as specified in Section 7.8.

To detect the occurrence of AEs and SAEs, the physician should use non-direct neutral questioning of the subject at each post-dose clinical visit. Information of AEs and SAEs may also be given voluntarily by the subject at any time during the study.

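### The post-treatment safety call goes only to completers, so subjects who leave early have no scheduled contact after an untimed, best-effort Early Termination Visit and no stated end to AE collection

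*Protocol*

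**What the plan says.** Protocol 6.1.7 schedules the Visit 8 call "7 + 2 days after Visit 7, for subjects who complete the study". The call covers adverse events and concomitant medications. Table 6.1.1, and its copy in SAP 14.1, time it from Visit 7 only.

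Protocol 7.3 sets two collection windows, both opening at the first dose. AE collection is to "continue through the post-withdrawal follow-up phone call (i.e., 7 days after Visit 7"). SAE collection is to "continue 30 days after the subject's last dose of study drug", with no distinction between completers and others. For early leavers the same section says "For subjects who terminate early, all AEs and SAEs should be treated as medically appropriate", which concerns treatment and not data collection. It then provides for continued follow-up of a subject who "has an SAE within 30 days after Visit 7". Section 7.1 words the end of AE recording differently: "all AEs occurring up to study completion, must be recorded in the eCRF".

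Subjects who leave early have an Early Termination Visit (6.1.5, with its own column in Table 6.1.1). It includes an AE assessment, C-SSRS, ECG, laboratory tests, physical examination and vital signs. Sites are to try to bring the subject back for it, and 4.3 asks for the procedures where possible. Neither section gives a day relative to the last dose. Concomitant medications are collected "through the Post Withdrawal Follow-Up Phone Call (Visit 8) or early termination".

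Sections 4.3, 5.3 and 5.6 provide for withdrawal of subjects who cannot tolerate their dose. Section 3.1 projects a 20% dropout rate.

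**The concern.** The end of AE collection is tied to a call and a visit that early leavers do not have. The SAE window does apply to them, but nothing is scheduled to observe it once the Early Termination Visit is over, and that visit may not take place.

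Withdrawal for intolerance leads directly into this group. Subjects who may have reacted badly to the drug therefore have one untimed visit at most, while completers have a full visit and then a call. Safety and tolerability is a stated objective (Protocol 2.2), and section 1.1.3 says that no study of this d:l mixture has been completed in adults. At stake are the completeness of the SAE record and AE listings, and the chance of noticing a new problem soon after a subject stops.

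**Working it through.** The documents give no figure for the number of subjects outside the call. The check sets the provisions side by side and then counts.

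**1. Scheduled post-treatment contacts**

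| | Completer | Early leaver |
|---|---|---|
| Last visit | Visit 7, Day 36 ±2 | Early Termination Visit, best effort, no day stated |
| AE assessment there | Yes | Yes, if the visit takes place |
| Call afterwards | 7 to 9 days after Visit 7 | None |
| Stated end of AE collection | The Visit 8 call | None |
| Stated end of SAE collection | 30 days after last dose | 30 days after last dose |

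**2. Whether another section supplies the missing contact**

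- 7.8 requires AEs to be followed until they resolve, stabilize or are no longer clinically significant. It acts on events already known.
- 7.5.1 requires an SAE to be reported within 24 hours of the site learning of it, including after treatment. It schedules no enquiry.
- 4.3 requires efforts to reach a subject who misses a visit or does not answer the telephone, and notice of every early withdrawal to the Medical Monitor. It sets no dated contact after the Early Termination Visit.
- 6.1.6 allows unscheduled visits once a safety concern has been identified.

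None of these would find a new event that starts after the Early Termination Visit unless someone reports it.

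**3. Number of subjects**

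Inputs: 104 randomized per arm and 3 × 104 = 312 in total (Protocol 9.1), with 20% dropout (3.1, 9.1). Subjects without a Visit 8 call = dropout rate × 312.

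- Projected 20%: 0.20 × 312 = 62.4, about 62 (0.20 × 104 = 20.8, about 21 per arm if spread evenly).
- Assumed 10%: 0.10 × 312 = 31.2, about 31.
- Assumed 30%: 0.30 × 312 = 93.6, about 94.

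The sample size itself leaves room for 104 − 87 = 17 losses per arm, or 51 in all (17/104 = 16.3%), which lies inside this range.

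**4. The rest of the 30 days for completers**

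Assume that the last dose falls at about Visit 7. The call then leaves 30 − 9 = 21 to 30 − 7 = 23 days of the SAE window with no scheduled contact. That later stretch is therefore uncovered for completers as well.

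**The case against.** The strongest reply is that the plan is more protective than a reading of 6.1.7 alone suggests. Most of that reply stands, and it limits the point in five ways.

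- **A reader might infer that early leavers have no scheduled contact in the 30-day SAE window.** The documents do not support this. The Early Termination Visit is planned, is fuller than the Visit 8 call, and would usually fall on or after the last dose. The gap begins after that visit, or at withdrawal if the visit is missed.
- **A reader might infer that the events that caused withdrawal go unfollowed.** They are known events, and 7.8 covers them whether or not the subject completed. Only new-onset events are exposed.
- **A reader might infer a biased comparison between arms.** This is not shown. The documents give no dropout by arm or by reason, and safety analysis is descriptive. Under SAP 8.4 an early terminator's AE more than 24 hours after the last dose is not treatment-emergent. Most events found by an added call would enter the listings and not the treatment-emergent tables.
- **A reader might infer that SAE collection has conflicting end dates.** Section 7.3 gives SAE collection one anchor, the last dose. The sentence on 30 days after Visit 7 concerns continued follow-up, and study completion in 7.1 can be read as the Visit 8 call. For early leavers, however, neither Visit 7 nor Visit 8 exists, so the wording needs reconciling. Nor does 5.9.2 show that AE collection stops at early termination, because it concerns concomitant medications.
- **A reader might want a further contact at day 30.** Section 7.3 defines a collection window and does not promise active enquiry at its end. Completers share that gap, so it is a matter of preference.

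The reply leaves two facts in place: AE collection has no stated end for early leavers, and nothing is scheduled after a visit that is neither dated nor assured.

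**Conclusion.** The point holds as a gap in safety data collection that is cheap to close. Early leavers have no scheduled contact after the Early Termination Visit and no stated end of AE collection. From then to day 30, new AEs and SAEs reach the database only by spontaneous report.

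At the projected dropout this concerns up to about 62 of 312 subjects, or 31 to 94 over an assumed 10% to 30%. The count is an upper bound on what a call could recover, because it includes subjects lost to follow-up or unwilling to be contacted. The share who leave for intolerance is not in the documents. The primary efficacy analysis is unaffected and the treatment-emergent AE tables would change little. The benefit lies in SAE capture, the AE listings and subject safety.

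**What to change.** In Protocol 6.1.7 and Table 6.1.1 (and the copy in SAP 14.1), make the existing Visit 8 call for every dosed subject. For completers it stays at 7 (+2) days after Visit 7. For the others it falls 7 (+2) days after the last dose or the Early Termination Visit, and the amendment should name one of the two.

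In Protocol 7.1 and 7.3, reconcile the three end points now in use (study completion, Visit 7, last dose) by anchoring AE and SAE collection to the last dose for all subjects. State the end of AE collection for early leavers explicitly.

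The cost is a short amendment, up to about 62 extra calls by existing site staff at the projected dropout, and slightly more AEs on record, mainly among early leavers.
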